## 16.2.2 Table A2 Management of GI irAEs in Patients Treated With ICPis

2.0 GI Toxicities	
2.1 Colitis	
Definition: A disorder characterized by inflammation of the colon Diagnostic work-up	

G2 Work-up of blood (CBC, comprehensive metabolic panel, TSH, ESR, CRP), stool (culture, Clostridium difficile, parasite, CMV or other viral etiology, ova and parasite) should be performed Consider testing for lactoferrin (for patient stratification to determine who needs more urgent endoscopy) and calprotectin (to follow-up on disease activity) Screening laboratories (HIV, hepatitis A and B, and blood quantiferon for TB) to prepare patients to start infliximab should be routinely done in patients at high risk for those infections and appropriately selected patients based on infectious disease expert's evaluation Imaging (eg, CT scan of abdomen and pelvis and GI endoscopy with biopsy) should be considered as there is evidence showing that the presence of ulceration in the colon can predict a corticosteroid-refractory course, which may require early infliximab Consider repeating endoscopy for patients who do not respond to immunosuppressive agents; repeating endoscopy for disease monitoring can be considered when clinically indicated and when planning to resume therapy
	

G3-4 All the work-up listed for G2 (blood, stool, imaging, and scope with biopsy) should be completed immediately Consider repeating endoscopy for patients who do not respond to immunosuppressive agents; repeating endoscopy for disease monitoring should only be considered when clinically indicated and when planning to resume ICPi
	
Grading (based on CTCAE for diarrhea, as most often used clinically)	Management
All patients	
Counsel all patients to be aware of and inform their health care provider immediately if they experience: Abdominal pain, nausea, cramping, blood or mucus in stool or changes in bowel habits, fever, abdominal distention, obstipation, constipation
 
For G2 or higher, consider permanently discontinuing CTLA-4 agents and may restart PD-1, PD-L1 agents if patient can recover to G1 or less; concurrent immunosuppressant maintenance therapy should be considered only if clinically indicated in individual cases

G1: Increase of fewer than four stools per day over baseline; mild increase in ostomy output compared with baseline	
Continue ICPi; alternatively, ICPi may be held temporarily and resumed if toxicity does not exceed G1
 
Monitor for dehydration and recommend dietary changes Facilitate expedited phone contact with patient/caregiver May obtain gastroenterology consult for prolonged G1 cases

G2: Increase of four to six stools per day over baseline; moderate increase in ostomy output compared with baseline	
Should hold ICPi temporarily until patient's symptoms recover to G1; can consider permanently discontinuing CTLA-4 agents and may restart PD-1, PD-L1 agents if patient can recover to G1 or less
 
Concurrent immunosuppressant maintenance therapy (, 10 mg prednisone equivalent dose) may be offered only if clinically indicated in individual cases

2.0 GI Toxicities	
	
May also include supportive care with medications such as Imodium if infection has been ruled out
 
Should consult with gastroenterology for G2 or higher
 
Administer corticosteroids, unless diarrhea is transient, starting with initial dose of 1 mg/kg/day prednisone or equivalent
 
When symptoms improve to G1 or less, taper corticosteroids over at least 4-6 weeks before resuming treatment, although resuming treatment while on low-dose corticosteroid may also be an option after an evaluation of the risks and benefits
 
EGD/colonoscopy, endoscopy evaluation should be highly recommended for cases Grade 2 to stratify patients for early treatment with infliximab based on the endoscopic findings and to determine the safety of resuming PD-1, PD-L1 therapy
 
Stool inflammatory markers can be considered (lactoferrin and calprotectin) in cases of G2 or higher to differentiate functional versus inflammatory diarrhea, and use calprotectin to monitor treatment response if provider prefers
 
Repeat colonoscopy is optional for cases of G2 or higher for disease activity monitoring to achieve complete remission, especially if there is a plan to resume ICPi

G3: Increase of seven or more stools per day over baseline, incontinence, hospitalization indicated, severe increase in ostomy output compared with baseline, limiting self-care ADL	
Should consider permanently discontinuing CTLA-4 agents and may restart PD-1, PD-L1 agents if patient can recover to G1 or less.
 
Administer corticosteroids (initial dose of 1-2 mg/kg/d prednisone or equivalent)
 
Consider hospitalization or outpatient facility for patients with dehydration or electrolyte imbalance
 
If symptoms persist 3-5 days or recur after improvement, consider administering IV corticosteroid or noncorticosteroid (eg, infliximab)
 
Consider colonoscopy in cases where patients have been on immunosuppression and may be at risk for opportunistic infections as an independent cause for diarrhea (ie, CMV colitis) and for those who are anti-TNF or corticosteroid refractory

G4: Life-threatening consequences; urgent intervention indicated	
Permanently discontinue treatment
 
Should admit patient when clinically indicated; patients managed as outpatients should be very closely monitored
 
Administer 1-2 mg/kg/d methylprednisolone or equivalent until symptoms improve to G1, and then start taper over 4-6 weeks
 
Consider early infliximab 5-10 mg/kg if symptoms refractory to corticosteroid within 2-3 days Consider lower GI endoscopy if symptoms are refractory despite treatment or there is concern of new infections

Additional considerations
 
The use of vedolizumab may be considered in patients refractory to infliximab and/or contraindicated to TNF-<math>\alpha</math> blocker. The decision should be made on an individual basis from gastroenterology and oncology evaluation. This is based on case series showing promising results
	

2.0 GI Toxicities	

Patients with hepatitis and irAE colitis are rare, and management should include permanently discontinuing ICPI and offering other immunosuppressant agents that work systemically for both conditions
 
Currently, enteritis alone as the cause of diarrhea is uncommon and requires small bowel biopsy as the evaluation tool. It may be managed similar as colitis, including corticosteroid and/or infliximab, etc
	
2.2 Hepatitis	

Definition: A disorder characterized by a viral pathologic process involving the liver parenchyma
 
Diagnostic work-up
 
Monitor patient for abnormal liver blood tests: AST, ALT, and bilirubin prior to each infusion and/or weekly if G1 liver function test elevations. No treatment is recommended for G1 liver function test abnormality
 
For G2 or higher:
 
Work-up for other causes of elevated liver enzymes should be tested, viral hepatitis, alcohol history, iron study, thromboembolic event, liver ultrasound, cross-sectional imaging for potential liver metastasis from primary malignancy. If suspicion for primary autoimmune hepatitis is high, can consider ANAs, antismooth muscle antibodies, antineutrophil cytoplasmic antibodies. If patients with elevated alkaline phosphatase alone, g-glutamyl transferase should be tested. For isolated elevation of transaminases, consider checking CK for other etiologies
	
Grading	Management
All patients	
Counsel all patients to be aware of and inform their health care provider immediately if they experience:
 
Yellowing of skin or whites of the eyes Severe nausea or vomiting
 
Pain on the right side of the abdomen Drowsiness
 
Dark urine (tea colored)
 
Bleeding or bruising more easily than normal Feeling less hungry than usual

G1: Asymptomatic (AST or ALT > ULN to 3.0 x ULN and/or total bilirubin > ULN to 1.5 x ULN)	
Continue ICPI with close monitoring; consider alternate etiologies
 
Monitor laboratories one to two times weekly
 
Manage with supportive care for symptom control

G2: Asymptomatic (AST or ALT > 3.0 to ≤ 5 x ULN and/or total bilirubin > 1.5 to ≤ 3 x ULN)	
Hold ICPI temporarily and resume if recover to G1 or less on prednisone ≤ 10 mg/d
 
For Grade 2 hepatic toxicity with symptoms, may administer corticosteroid 0.5-1 mg/kg/d prednisone or equivalent if the abnormal elevation persists with significant clinical symptoms in 3-5 days Increase frequency of monitoring to every 3 days
 
Infliximab might not be the most appropriate treatment option in the situation of immune-mediated hepatitis given the potential risk of idiosyncratic liver failure (Note: No clear evidence shows the liver toxicity from infliximab from other studies)
 
In follow-up, may resume ICPI treatment followed by taper only when symptoms improve to G1 or less and corticosteroid ≤ 10 mg/d; taper over at least 1 month
 
Patients should be advised to stop unnecessary medications and any known hepatotoxic drugs

G3: Symptomatic liver dysfunction, fibrosis by biopsy, compensated cirrhosis, reactivation of chronic hepatitis (AST or ALT 5-20 x ULN and/or total bilirubin 3-10x ULN)	
Permanently discontinue ICPI
 
Immediately start corticosteroid 1-2 mg/kg methylprednisolone or equivalent
 
If corticosteroid refractory or no improvement after 3 days, consider mycophenolate mofetil or azathioprine (if using azathioprine should test for thiopurine methyltransferase deficiency)

2.0 GI Toxicities	
	
Laboratories at daily or every other day; consider inpatient monitoring for patients with AST/ALT > 8 x ULN and/or elevated TB 3 x ULN
 
Increase frequency of monitoring to every 1-2 days
 
Infliximab might not be the most appropriate treatment option in the situation of immune-mediated hepatitis given the potential risk of liver failure (Note: No clear evidence shows that the liver toxicity from infliximab from other studies); alternatives include non-TNF-<math>\alpha</math> agents as systemic immunosuppressants. If no improvement is achieved with corticosteroids or for patients on combination therapy with a novel agent, with standard chemotherapy, or with targeted therapy, refer to hepatologist for further pathologic evaluation of hepatitis
 
Corticosteroid taper can be attempted around 4-6 weeks; re-escalate if needed; optimal duration unclear

G4: Decompensated liver function (eg, ascites, coagulopathy, encephalopathy, coma; AST or ALT > 20 x ULN and/or total bilirubin > 10 x ULN)	
Permanently discontinue ICPI
 
Administer 2 mg/kg/d methylprednisolone equivalents
 
If corticosteroid refractory or no improvement after 3 days, consider mycophenolate mofetil
 
Monitor laboratories daily; consider inpatient monitoring
 
Avoid the use of infliximab in the situation of immune-mediated hepatitis
 
Hepatology consult if no improvement was achieved with corticosteroid
 
Corticosteroid taper can be attempted around 4-6 weeks when symptoms improve to G1 or less; re-escalate if needed; optimal duration unclear
 
Consider transfer to tertiary care facility if necessary

All recommendations are expert consensus based, with benefits outweighing harms, and strength of recommendations is moderate.
 
Abbreviations: ADL, activities of daily living; ALT, alanine aminotransferase; ANA, antinuclear antibody; AST, aspartate aminotransferase; CBC, complete blood count; CK, creatine kinase; CMV, cytomegalovirus; CRP, C-reactive protein; CT, computed tomography; CTCAE, Common Terminology Criteria for Adverse Events; CTLA-4, cytotoxic T-cell lymphocyte-4; EGD, esophagogastroduodenoscopy; ESR, erythrocyte sedimentation rate; G, Grade; GI, gastrointestinal; HIV, human immunodeficiency virus; ICPI, immune checkpoint inhibitor; irAE, immune-related adverse event; IV, intravenous; PD-1, programmed death 1; PD-L1, programmed death ligand 1; TB, tuberculosis; TNF, tumor necrosis factor; TSH, thyroid-stimulating hormone; ULN, upper limit of normal.
	

## 16.2.3 Table A3 Management of Lung irAEs in Patients Treated With ICPi

3.0 Lung Toxicities	
3.1 Pneumonitis	

Definition: Focal or diffuse inflammation of the lung parenchyma (typically identified on CT imaging)            No symptomatic, pathologic, or radiographic features are pathognomonic for pneumonitis            Diagnostic work-up            Should include the following: CXR, CT, pulse oximetry            For G2 or higher, may include the following infectious work-up: nasal swab, sputum culture and sensitivity, blood culture and sensitivity, urine culture and sensitivity
	
Grading	Management
G1: Asymptomatic, confined to one lobe of the lung or < 25% of lung parenchyma, clinical or diagnostic observations only	
Hold ICPi with radiographic evidence of pneumonitis progression            May offer one repeat CT in 3-4 weeks; in patients who have had baseline testing, may offer a repeat spirometry/DLCO in 3-4 weeks            May resume ICPi with radiographic evidence of improvement or resolution. If no improvement, should treat as G2            Monitor patients weekly with history and physical examination and pulse oximetry; may also offer CXR

G2: Symptomatic, involves more than one lobe of the lung or 25%-50% of lung parenchyma, medical intervention indicated, limiting instrumental ADL	
Hold ICPi until resolution to G1 or less            Prednisone 1-2 mg/kg/d and taper by 5-10 mg/wk over 4-6 weeks Consider bronchoscopy with BAL            Consider empirical antibiotics            Monitor every 3 days with history and physical examination and pulse oximetry, consider CXR; no clinical improvement after 48-72 hours of prednisone, treat as G3

G3: Severe symptoms, hospitalization required, involves all lung lobes or 50% of lung parenchyma, limiting self-care ADL, oxygen indicated G4: Life-threatening respiratory compromise, urgent intervention indicated (intubation)	
Permanently discontinue ICPi            Empirical antibiotics; (methyl)prednisolone IV 1-2 mg/kg/d; no improvement after 48 hours, may add infliximab 5 mg/kg or mycophenolate mofetil IV 1 g twice a day or IVIG for 5 days or cyclophosphamide; taper corticosteroids over 4-6 weeks            Pulmonary and infectious disease consults if necessary            Bronchoscopy with BAL 6 transbronchial biopsy            Patients should be hospitalized for further management


Additional considerations            GI and Pneumocystis prophylaxis with PPI and Bactrim may be offered to patients on prolonged corticosteroid use (> 12 weeks), according to institutional guidelines            Consider calcium and vitamin D supplementation with prolonged corticosteroid use            The role of prophylactic fluconazole with prolonged corticosteroid use (> 12 weeks) remains unclear, and physicians should proceed according to institutional guidelines            Bronchoscopy + biopsy; if clinical picture is consistent with pneumonitis, no need for biopsy            All recommendations are expert consensus based, with benefits outweighing harms, and strength of recommendations are moderate.            Abbreviations: ADL, activities of daily living; BAL, bronchoalveolar lavage; CT, computed tomography; CXR, chest x-ray; DLCO, diffusing capacity of lung for carbon monoxide; G, Grade; GI, gastrointestinal; ICPi, immune checkpoint inhibitor; irAE, immune-related adverse event; IV, intravenous; IVIG, intravenous immunoglobulin; PPI, proton pump inhibitor.
	

## 16.2.4 Table A4 Management of Endocrine irAEs in Patients Treated With ICPis

4.0 Endocrine Toxicity	
Counsel patients to inform their health care provider immediately if they experience any changes in their health since their last visit, especially any of the following:	
Headaches that will not go away or unusual headache patterns Vision changes Rapid heartbeat Increased sweating Extreme tiredness or weakness Muscle aches Weight gain or weight loss Dizziness or fainting Feeling more hungry or thirsty than usual Hair loss Changes in mood or behavior, such as decreased sex drive, irritability, or forgetfulness Feeling cold Constipation Voice gets deeper Urinating more often than usual Nausea or vomiting Abdominal pain	
4.1 Thyroid	
4.1.1 Primary hypothyroidism	
Definition: Elevated TSH, normal or low FT4	
Diagnostic work-up	
TSH and FT4 every 4-6 weeks as part of routine clinical monitoring on therapy or for case detection in symptomatic patients	
Grading	Management
G1: TSH < 10 mIU/L and asymptomatic G2: Moderate symptoms; able to perform ADL; TSH persistently > 10 mIU/L	Should continue ICPi with close follow-up and monitoring of TSH, FT4 May hold ICPi until symptoms resolve to baseline Consider endocrine consultation Prescribe thyroid hormone supplementation in symptomatic patients with any degree of TSH elevation or in asymptomatic patients with TSH levels that persist > 10 mIU/L (measured 4 weeks apart) Monitor TSH every 6-8 weeks while titrating hormone replacement to normal TSH FT4 can be used in the short term (2 weeks) to ensure adequacy of therapy in those with frank hypothyroidism where the FT4 was initially low Once adequately treated, should monitor thyroid function (at least TSH) every 6 weeks while on active ICPi therapy or as needed for symptoms to ensure appropriate replacement; repeat testing annually or as indicated by symptoms once stable
G3-4: Severe symptoms, medically significant or life-threatening consequences, unable to perform ADL	Hold ICPi until symptoms resolve to baseline with appropriate supplementation Endocrine consultation

4.0 Endocrine Toxicity	
	May admit for IV therapy if signs of myxedema (bradycardia, hypothermia) Thyroid supplementation and reassessment as in G2

Additional considerations
 
For patients without risk factors, full replacement can be estimated with an ideal body weight–based dose of approximately 1.6 µg/kg/d
 
For elderly or fragile patients with multiple comorbidities, consider titrating up from low dose, starting at 25-50 mg
 
Extreme elevations of TSH can be seen in the recovery phase of thyroiditis and can be watched in asymptomatic patients to determine whether there is recovery to normal within 3-4 weeks
 
Under guidance of endocrinology, consider tapering hormone replacement and retesting in patients with a history of thyroiditis (initial thyrotoxic phase)
 
Adrenal dysfunction, if present, must always be replaced before thyroid hormone therapy is initiated
	
4.1.2 Hyperthyroidism	

Definition: Suppressed TSH and high normal or elevated FT4 and/or triiodothyronine
 
Diagnostic work-up
 
Monitor TSH, FT4 every 4-6 weeks from the start of therapy or as needed for case detection in symptomatic patients
 
Consider TSH receptor antibodies if there are clinical features and suspicion of Grave disease (eg, ophthalmopathy)
 
Close monitoring of thyroid function every 2-3 weeks after diagnosis to catch transition to hypothyroidism in patients with thyroiditis and hyperthyroidism
	
Grading	Management
G1: Asymptomatic or mild symptoms	
Can continue ICPI with close follow-up and monitoring of TSH, FT4 every 2-3 weeks until it is clear whether there will be persistent hyperthyroidism (see below) or hypothyroidism (see 4.1.1)
 
Consider holding ICPI until symptoms return to baseline
 
Consider endocrine consultation
 
b-Blocker (eg, atenolol, propranolol) for symptomatic relief
 
Hydration and supportive care
 
Corticosteroids are not usually required to shorten duration
 
For persistent hyperthyroidism (> 6 weeks) or clinical suspicion, work-up for Graves disease (TSI or TRAB) and consider thionamide (methimazole or PTU) Refer to endocrinology for Graves disease

G3-4: Severe symptoms, medically significant or life-threatening consequences, unable to perform ADL	
Hold ICPI until symptoms resolve to baseline with appropriate therapy
 
Endocrine consultation
 
b-Blocker (eg, atenolol, propranolol) for symptomatic relief
 
For severe symptoms or concern for thyroid storm, hospitalize patient and initiate prednisone 1-2 mg/kg/d or equivalent tapered over 1-2 weeks; consider also use of SSKI or thionamide (methimazole or PTU).

Additional considerations
 
Thyroiditis is transient and resolves in a couple of weeks to primary hypothyroidism or normal. Hypothyroidism can be treated as above. Graves disease is generally persistent and is due to increased thyroid hormone production that can be treated with antithyroid medical therapy. Physical examination findings of ophthalmopathy or thyroid bruit are diagnostic of Graves and should prompt early endocrine referral.
	
4.2 Adrenal – primary adrenal insufficiency	

4.0 Endocrine Toxicity	
Definition: Adrenal gland failure leading to low morning cortisol, high morning ACTH, as well as hyponatremia and hyperkalemia with orthostasis and volume depletion due to loss of aldosterone	
Diagnostic work-up for patients in whom adrenal insufficiency is suspected: Evaluate ACTH (AM), cortisol level (AM) Basic metabolic panel (Na, K, CO 2 , glucose) Consider ACTH stimulation test for indeterminate results If primary adrenal insufficiency (high ACTH, low cortisol) is found biochemically: Evaluate for precipitating cause of crisis such as infection Perform an adrenal CT for metastasis/hemorrhage	
Grading	Management
G1: Asymptomatic or mild symptoms	Consider holding ICPi until patient is stabilized on replacement hormone Endocrine consultation Replacement therapy with prednisone (5-10 mg daily) or hydrocortisone (10-20 mg orally every morning, 5-10 mg orally in early afternoon) May require fludrocortisone (0.1 mg/d) for mineralocorticoid replacement in primary adrenal insufficiency Titrate dose up or down as symptoms dictate
G2: Moderate symptoms, able to perform ADL	Consider holding ICPi until patient is stabilized on replacement hormone Endocrine consultation Initiate outpatient treatment at two to three times maintenance (if prednisone, 20 mg daily; if hydrocortisone, 20-30 mg in the morning, and 10-20 mg in the afternoon) to manage acute symptoms. Taper stress-dose corticosteroids down to maintenance doses over 5-10 days Maintenance therapy as in G1.
G3-4: Severe symptoms, medically significant or life-threatening consequences, unable to perform ADL	Hold ICPi until patient is stabilized on replacement hormone Endocrine consultation See in clinic or, for after hours, make an emergency department referral for normal saline (at least 2 L) and IV stress-dose corticosteroids on presentation (hydrocortisone 100 mg or dexamethasone 4 mg (if the diagnosis is not clear and stimulation testing will be needed) Taper stress-dose corticosteroids down to maintenance doses over 7-14 days after discharge Maintenance therapy as in G1
Additional considerations Primary and secondary adrenal insufficiency can be distinguished by the relationship between ACTH and cortisol. If the ACTH is low with low cortisol, then management is as per 4.3. Patients on corticosteroids for management of other conditions will have low morning cortisol as a result of iatrogenic, secondary adrenal insufficiency. ACTH will also be low in these patients. A diagnosis of adrenal insufficiency is challenging to make in these situations (see next section on hypophysitis).	

4.0 Endocrine Toxicity	

Emergent therapy for someone with suspected adrenal insufficiency is best done with dexamethasone as a stimulation test can still be performed. If the diagnosis is already confirmed, can use hydrocortisone 100 mg.
 
All patients need education on stress dosing and a medical alert bracelet for adrenal insufficiency to trigger stress-dose corticosteroids by EMS.
 
Endocrine consultation prior to surgery or any procedure for stress-dose planning.
	
4.3 Pituitary - hypophysitis	

Definition: Inflammation of the pituitary with varying effects on hormone function. Most commonly presenting with central adrenal insufficiency. May also have central hypothyroidism, diabetes insipidus, and hypogonadism.
 
Diagnostic work-up
 
Diagnosis: Low ACTH with a low cortisol. Low or normal TSH with a low FT4. Hypernatremia and volume depletion with diabetes insipidus. Low testosterone or estradiol with low LH and FSH.
 
Testing:
 
Evaluate ACTH, cortisol (AM), TSH, FT4, electrolytes
 
Consider evaluating LH, FSH, and testosterone levels in males or estrogen in premenopausal females with fatigue, loss of libido, and mood changes Consider MRI of the brain with or without contrast with pituitary/sellar cuts in patients with multiple endocrine abnormalities 6 new severe headaches or complaints of vision changes
	
Grading	Management
G1: Asymptomatic or mild symptoms	
Consider holding ICPi until patient is stabilized on replacement hormones
 
Endocrine consultation
 
Hormonal supplementation as in G1

G3-4: Severe symptoms, medically significant or life-threatening consequences, unable to perform ADL	
Hold ICPi until patient is stabilized on replacement hormones
 
Endocrine consultation
 
Hormonal supplementation as in G1
 
Consider initial pulse dose therapy with prednisone 1-2 mg/kg oral daily (or equivalent) tapered over at least 1-2 weeks

Additional considerations
 
Be aware of the need to start corticosteroids first when planning hormone replacement therapy for multiple deficiencies
 
All patients need instruction on doubling doses for illness (stress dosing) and a medical alert bracelet for adrenal insufficiency to trigger stress-dose corticosteroids by EMS
 
Corticosteroid use can cause isolated central adrenal insufficiency
 
Work-up cannot be done with a simple AM cortisol in a patient on corticosteroids for other conditions
 
Laboratory confirmation of adrenal insufficiency should not be attempted until treatment with corticosteroids for other disease is ready to be discontinued. For long-term exposure, consult endocrinology for recovery and weaning protocol using hydrocortisone.
	
4.4 Diabetes	

Definition: T2DM is a combination of insulin resistance and insufficiency that may require oral or insulin therapy. It may be new onset or exacerbated during therapy for nonimmunologic reasons, such as corticosteroid exposure.
 
Autoimmune T1DM results from islet cell destruction and is often acute onset, with ketosis and an insulin requirement
 
Diagnostic work-up
 
Monitor patients for hyperglycemia or other signs and symptoms of new or worsening DM, including measuring glucose at baseline and with each treatment cycle during induction for 12 weeks, then every 3-6 weeks thereafter.
 
To guide the work-up in new-onset hyperglycemia, clinicians should consider a patient's medical background, exposure history, and risk factors for each subtype of DM.
 
Laboratory evaluation in suspected T1DM should include testing for ketosis in urine and an assessment of the anion gap on a metabolic panel. Anti-glutamic acid decarboxylase, anti-islet cell, or anti-insulin antibodies are highly specific for autoimmune diabetes. Insulin and C-peptide levels can also assist in the diagnosis.
	

4.0 Endocrine Toxicity	
Grading	Management
G1: Asymptomatic or mild symptoms; fasting glucose value > ULN (160 mg/dL); fasting glucose value > ULN (8.9 mmol/L); no evidence of ketosis or laboratory evidence of T1DM	Can continue ICPI with close clinical follow-up and laboratory evaluation May initiate oral therapy for those with new-onset T2DM Screen for T1DM if appropriate, for example, acute onset with prior normal values or clinical concern for ketosis
G2: Moderate symptoms, able to perform ADL, fasting glucose value > 160-250 mg/dL; fasting glucose value > 8.9-13.9 mmol/L, ketosis or evidence of T1DM at any glucose level	May hold ICPI until glucose control is obtained Titrate oral therapy or add insulin for worsening control in T2DM Should administer insulin for T1DM (or as default therapy if there is confusion about type) Urgent endocrine consultation for any patient with T1DM; in the absence of endocrinology, internal medicine may suffice Consider admission for T1DM if early outpatient evaluation is not available or signs of ketoacidosis are present
G3-4: Severe symptoms, medically significant or life-threatening consequences, unable to perform ADL G3: > 250-500 mg/dL (> 13.9-27.8 mmol/L) G4: > 500 mg/dL (> 27.8 mmol/L)	Hold ICPI until glucose control is obtained on therapy with reduction of toxicity to G1 or less Urgent endocrine consultation for all patients Initiate insulin therapy for all patients Admit for inpatient management: Concerns for developing DKA, Symptomatic patients regardless of diabetes type, New-onset T1DM unable to see endocrinology

Additional considerations
 
Insulin therapy can be used as the default in any case with hyperglycemia
 
Long-acting therapy alone is not usually sufficient for T1DM, where half of daily requirements are usually given in divided doses as prandial coverage and half as long acting.
 
Insulin doses will be lower in T1DM because of preserved sensitivity (total daily requirement can be estimated at 0.3-0.4 units/kg/d).
 
In T2DM, sliding-scale coverage with meals over a few days provides data to estimate a patient's daily requirements and can be used to more rapidly titrate basal needs.
 
All recommendations are expert consensus based, with benefits outweighing harms, and strength of recommendations are moderate.
 
Abbreviations: ACTH, adrenocorticotropic hormone; ADL, activities of daily living; CT, computed tomography; DKA, diabetic ketoacidosis; DM, diabetes mellitus; EMS, emergency medical services; FSH, follicle-stimulating hormone; FT4, free thyroxine; G, Grade; ICPI, immune checkpoint inhibitor; irAE, immune-related adverse event; LH, luteinizing hormone; MRI, magnetic resonance imaging; PTU, propylthiouracil; 2L, second-line; SSKI, potassium iodide; T1DM, type 1 diabetes mellitus; T2DM, type 2 diabetes mellitus; TRAb, thyroid-stimulating hormone receptor antibody; TSH, thyroid-stimulating hormone; TSI, thyroid-stimulating immunoglobulin; ULN, upper limit of normal.
	

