**Table 2: Management of immune- mediated adverse events**

Immune-related AEs are specific to immunotherapies and vary by organ system. The following immune-related AEs are important identified risks for M7824:
 
 
• Immune-related pneumonitis
 
• Immune-related hepatitis
 
• Immune-related colitis
 
• Immune-related nephritis and renal dysfunction
 
• Immune-related endocrinopathies
 
• (thyroid disorders, adrenal insufficiency, type 1 diabetes mellitus, pituitary disorders)
 
• Immune related rash
 
• Other immune-related events (myositis, myocarditis, encephalitis)
 
 
The following immune-related AEs are important potential risks for M7824:
 
 
• Guillain-Barré syndrome
 
• Uveitis
 
• Pancreatitis
 
• Myasthenia gravis/myasthenic syndrome
 
 
Recommended guidance and management for specific irAEs are provided in the current National Comprehensive Cancer Network (NCCN) guideline available at http://www.nccn.org.
 
Requirements in addition to NCCN guidelines:
 
 
• Permanent treatment discontinuation is required in case of immune-related Grade 4 rash/inflammatory dermatitis, nephritis, autoimmune hemolytic anemia, hemolytic uremic
 

--

syndrome, aplastic anemia, immune thrombocytopenia, acquired thrombotic thrombocytopenic purpura inflammatory arthritis, myositis and polymyalgia-like syndrome.

- For Grade 4 immune-related lymphopenia, permanent treatment discontinuation will be required, if lymphopenia is considered immune-related in nature, no clear alternative explanation exists for the event, and it does not resolve within 14 days. Permanent treatment discontinuation is not required when the AE is manifested by a single laboratory value out of normal range without any clinical correlates. In this case, treatment should be held until the etiology is determined. If the event is not considered immune-related and resolves to Grade  $\leq 1$ , restarting treatment may be considered.
- For Grade 1 immune-related pneumonitis: continue treatment. If clinically indicated, monitor participants weekly or more frequently as needed with history, physical examination and pulse oximetry. If symptoms appear and/or changes in the physical exam are noted, treat as Grade 2.

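### Appendix C, Table A4 prints a low starting dose of thyroid hormone in milligrams beside a full replacement dose in micrograms per kg, and the two cannot both hold

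*Combined protocol and SAP*

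**What the plan says.** Appendix C of the protocol sets out management of immune-related adverse events by organ system. Table A4 (section 16.2.4) covers endocrine toxicity, and its section 4.1.1 covers primary hypothyroidism. For Grade 2 the table says "Prescribe thyroid hormone supplementation in symptomatic patients with any degree of TSH elevation", or where TSH stays raised without symptoms. The row of additional considerations then gives two dosing statements, one directly after the other:

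- The first applies where no risk factors are present and says that "full replacement can be estimated with an ideal body weight–based dose of approximately 1.6 µg/kg/d".
- The second turns to more cautious dosing and reads as follows: "For elderly or fragile patients with multiple comorbidities, consider titrating up from low dose, starting at 25-50 mg".

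Neither sentence names a product. The second prints no per-day or per-kg unit. No other section restates or corrects the starting dose.

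Table 2 in section 3.3.1.4 lists immune-related endocrinopathies among the important identified risks of M7824 and specifies "thyroid disorders, adrenal insufficiency, type 1 diabetes mellitus, pituitary disorders". Section 14.1.2 names hypothyroidism among the identified immune-related risks, and the study calendar (Appendix A, footnote 5) includes TSH in the laboratory panel.

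**The concern.** The second sentence is written as the cautious alternative to the first: a patient who may not tolerate full replacement begins lower and works upward. As printed, the cautious dose is in milligrams and the full dose is in micrograms per kg, which reverses their order by two to three orders of magnitude.

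What is at stake is patient safety. Thyroid disorders are an expected toxicity of this drug, and scheduled TSH testing will bring cases to light. The trial admits patients with ECOG status up to 2 and creatinine clearance down to 30 mL/min/1.73 m² (section 2.1.1). Cohort 1A accepts impaired renal function or ECOG 2 as grounds for cisplatin ineligibility (section 2.1.2). Some participants are therefore plausibly the frail or comorbid patients whom the sentence addresses.

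**Working it through.** The plan gives no derived figure to reproduce here. The check is a unit conversion and a ratio.

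**Inputs from the documents (Table A4, section 4.1.1)**
- Full replacement: 1.6 µg per kg of ideal body weight per day.
- Low starting dose: 25-50 mg.

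**Assumptions, not in the documents**
- The 25-50 mg is a daily dose.
- Ideal body weight is 50-100 kg, with 70 kg as the central case.
- Both sentences concern the same hormone. Their placement under one heading supports this.

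**Conversion**

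25 mg × 1,000 = 25,000 µg; 50 mg × 1,000 = 50,000 µg.

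**Ratio of low dose to full dose** = (25,000 or 50,000 µg) / (1.6 × weight in kg)

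| Ideal body weight | Full dose (1.6 × kg) | 25 mg / full dose | 50 mg / full dose |
|---|---|---|---|
| 50 kg | 80 µg/d | 312.5 | 625 |
| 70 kg | 112 µg/d | 223.2 | 446.4 |
| 100 kg | 160 µg/d | 156.2 | 312.5 |

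Over 50-100 kg the printed low dose is therefore about 156 to 625 times full replacement.

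**Does the conclusion depend on the assumed weight?** For 25 mg merely to equal the full daily dose, ideal body weight would have to be 25,000 / 1.6 = 15,625 kg. It does not.

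**Does it depend on the daily reading?** At 70 kg, 25 mg equals 25,000 / 112 = about 223 days of full replacement. No ordinary dosing interval would reconcile the sentences. Reading the figure as per kg would widen the gap.

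**The case against.** **The fault may lie in the extracted text.** Appendix C has several damaged symbols. The beta of beta-blocker appears as a Latin b (4.1.2), and a gamma appears as a g (2.2). The alpha of TNF-alpha appears as a Latin a (5.1), and a hash sign stands before 10 mg (10.1). A stray digit 6 (3.1, 5.1) and a stray full stop (8.4) appear where operators seem intended. A lost Greek letter could produce this discrepancy. Against that, the µ was read correctly one sentence earlier and again in the platelet counts of 8.6, and TNF-alpha is intact in Tables A2 and A10. The pattern is mixed. It shows neither a reading fault nor an error on the sponsor's page. This objection stands as a reason to check the page before acting.

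**The reach is limited.** Table 2 sends staff to the NCCN guideline, section 3.3.1.2 does the same for symptomatic Grade 3-4 endocrinopathies, and section 3.3.1.8 relies on ASCO and NCCN. No section in the body cites Appendix C, and the table of contents ends at Appendix B. Table A4 suggests endocrine consultation at Grade 2 and lists it at Grades 3-4. A prescriber or pharmacist could well notice the mismatch. All of this makes literal use less likely. It does not make the two sentences consistent, and the tables are part of the protocol's own management guidance.

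**Two stronger readings are tempting.** A reader might infer that the protocol orders frail patients to be started on this dose. It does not: the sentence asks staff to consider titrating up. A reader might also infer that the trial's safety data will be distorted by thyroid overdoses. That would require the figure to be ordered, dispensed and taken literally, and nothing in the documents indicates that this has happened or will happen.

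**Conclusion.** The two sentences contradict each other as printed, and the contradiction holds at any human body weight. Its size, about 156 to 625 times full replacement (223 to 446 times at 70 kg), rests on the stated assumptions of a daily dose and an ideal body weight of 50-100 kg. It also depends on the source page printing what the extracted text shows.

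This is an internal unit inconsistency in supportive-care guidance. Its importance is the risk to a patient if the figure were followed literally. Safety is a secondary objective (section 1.1.2). The response endpoint, the Simon two-stage boundaries and the cohort sizes in section 10.2 are unaffected. The arithmetic shows that the sentences disagree; it does not show which of them, or which unit, is right.

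**What to change.** First check the source page of Table A4, section 4.1.1. If it prints matching units that make the two sentences consistent, withdraw the point.

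If the page prints what the extracted text shows, the sponsor should reconcile the two sentences in a single unit, with the dosing basis (per day, per kg) stated for both. The sponsor should verify the result against the source guideline, with the medical monitor and pharmacy, before reissue. Staff should be told of the discrepancy without waiting for the amended document. Since other symbols in Appendix C are damaged, the same pass can check those.

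The cost is a page check, a one-line correction in the next amendment with its usual IRB review, and a short notice to staff. No analysis, sample size or visit schedule changes.
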